#### 15.1. Serum Concentration Data

Participants with partial data will be evaluated on a case-by-case basis to determine if sufficient data are available for reliable estimation of PK parameters.

Whole blood samples will be collected for measurement of serum concentrations of VIS954 at the time points specified in protocol Section 1.3. A listing of PK blood sample collection times as well as derived sampling time deviations will be provided. Samples that are outside the protocol-specified collection windows (calculated from the time zero point [e.g., time of drug administration] or the last relevant activity) will be identified, as well as participants that are excluded from the PKAS.

Serum concentrations will be summarized using descriptive statistics by Japanese versus non-Japanese, ADA status (positive and negative) and overall, for each treatment group. Results for samples which were collected outside the specified collection window will be included in the descriptive statistics and will be included in the calculation of PK parameters unless otherwise warranted by the data (i.e., in case of a protocol deviation impacting the validity of the sample collected such as a predose sample collected after dosing, or a postdose sample collected prior to dosing, etc.), but such results will be flagged in the listing. Concentrations that are below the limit of quantitation (BLQ) will be treated as zero for the computation of descriptive statistics.

A by-treatment participant listing of all concentration-time data for each cohort will be presented. Figures of arithmetic mean concentration-time data (±SD, as appropriate) will be presented for each cohort, by Japanese versus non-Japanese and ADA status (positive and negative) within each treatment group on linear and semi-logarithmic scales. Individual participant concentration-time data will be graphically presented on linear and semi-logarithmic scales using different symbols for Japanese and non-Japanese participants. All concentrations of VIS954 which were found to be BLQ for the PK assay during analysis will be imputed to and plotted at the nominal value of the LLOQ (25 ng/mL, i.e. 0.025 ug/mL) for all graphs which use a semi-logarithmic scale axis.

#### 15.2. Pharmacokinetic Parameters

For PK parameter calculations, predose samples that are BLQ or missing will be assigned a numerical

Visterra Insert
Customer Name/ Logo
Protocol VIS954-101
Page 26 of 42

Statistical Analysis Plan

value of zero. Any anomalous concentration values observed at predose will be identified in the study report and used for the computation of PK parameters. Pharmacokinetic parameters will be computed if the anomalous concentration is not greater than 5% of the observed maximum concentration (Cmax). If the anomalous concentration is greater than 5% of Cmax, the PK parameters for the given participant will be calculated and reported in the listing but excluded from statistical summaries and analyses.

Any other BLQ concentrations will be assigned a value of zero if they precede quantifiable samples in the initial portion of the profile. A BLQ value that occurs between quantifiable data points, especially prior to  $C_{max}$ , will be evaluated to determine if an assigned concentration of zero makes sense, or if exclusion of the data is warranted. Following  $C_{max}$ , BLQ values embedded between 2 quantifiable data points will be treated as missing when calculating PK parameters. If a BLQ value occurs at the end of the collection interval (after the last quantifiable concentration), it will be set to zero. If consecutive BLQ concentrations are followed by quantifiable concentrations in the terminal portion of the concentration curve, these quantified values will be excluded from the PK analysis by setting them to missing, unless otherwise warranted by the concentration-time profile.

The following PK parameters will be estimated for VIS954 in serum by non-compartmental methods using actual elapsed time from dosing. A minimum of 3 quantifiable concentration-time data points will be required for calculation of PK parameters:

Cmax Maximum serum concentration (μg/mL), obtained directly from the

observed concentration versus time data.

tmax Time of maximum serum concentration (hr), obtained directly from the

observed concentration versus time data.

AUC0-last Area under the concentration-time curve in serum from predose to time of

last quantifiable concentration (hr\*µg/mL), calculated by linear up/log down

trapezoidal summation.

AUC0-inf Area under the concentration-time curve in serum from predose extrapolated

to infinite time (hr\* $\mu$ g/mL), calculated by linear up/log down trapezoidal summation and extrapolated to infinity by addition of the last quantifiable concentration divided by the elimination rate constant: AUC0-last + Clast/ $\lambda$ z.

 $t_{1/2}$  Apparent terminal half-life (hr), determined as  $\ln 2/\lambda_z$ .

CL/F Apparent clearance after extravascular dosing (L/hr), calculated as dose

divided by AUC0-inf.

Vd/F Apparent volume of distribution following extravascular dosing (L),

calculated as dose divided by  $[\lambda_z \cdot AUC_{0-inf}]$ 

DNCmax Dose normalized Cmax (μg/mL/mg)

DNAUC0-last Dose normalized AUC0-last (hr\*µg/mL/mg)

DNAUC0-inf Dose normalized AUC0-inf (hr\*µg/mL/mg)

The following PK parameters will be calculated for diagnostic purposes and listed but will not be summarized.

 $t_{1/2}$ , Interval The time interval (hr) of the log-linear regression to determine  $\lambda_z$ .

t1/2, N Number of data points included in the log-linear regression analysis to

determine  $\lambda_z$ . A minimum of 3 data points will be used for determination.

λz Apparent terminal rate constant (1/hr), determined by linear regression of

the terminal points of the log-linear concentration-time curve. Visual assessment will be used to identify the terminal linear phase of the concentration-time profile. A minimum of 3 data points will be used for

determination.

Adjusted Rsq Goodness of fit statistic for calculation of  $\lambda_z$  (Regression coefficient). If the

Adjusted Rsq value is less than 0.800 then AUC0-inf and t1/2 will be listed but

not summarized.

Page 28 of 42

[figure not shown]
Statistical Analysis Plan

%AUCex

Percentage of  $AUC_{0-inf}$  obtained by extrapolation, calculated as  $[(C_{last}/\lambda_z)/AUC_{0-inf}\times 100]$ . If the %AUCex is greater than 20% of AUC0-inf, then  $AUC_{0-inf}$  will be listed but not included in summary and inferential statistics. Associated parameters (CL/F and Vd/F) will be listed but not included in summary statistics as well.

Pharmacokinetic parameters will be summarized by each cohort and by Japanese versus non-Japanese within each active treatment group using descriptive statistics and listed by participant (as applicable). Geometric mean, and geometric CV% will not be calculated for tmax. Scatter plots of individual and geometric mean of PK parameters, Cmax, AUC0-last, AUC0-inf versus dose will be presented.

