# 5.5. Pharmacokinetic Analysis Set [PKAS]

The pharmacokinetic analysis set (PKAS) will consist of all participants who receive active study drug

Visterra Insert
Customer Name/ Logo
Protocol VIS954-101
Page 17 of 42

Statistical Analysis Plan

(VIS954) and have at least 1 measured post-dose VIS954 serum concentration at a scheduled PK time after start of dosing for at least 1 PK analyte without protocol deviations or events with potential to affect the evaluation of the PK data. Participants in this population will be used for all PK analyses.

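### The three-value minimum in SAP 15.2 should not cover Cmax and tmax: in a cohort with exposure close to the LLOQ it would bias the geometric mean Cmax upward

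*SAP*

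**What the plan says.** SAP 15.2 introduces its parameter list with the condition "A minimum of 3 quantifiable concentration-time data points will be required for calculation of PK parameters". The list opens with Cmax and tmax, and no exception is made for either. Their definitions are "Maximum serum concentration (μg/mL), obtained directly from the" and "Time of maximum serum concentration (hr), obtained directly from the" observed profile; neither involves a fitted slope.

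The terminal rate constant λz has its own requirement further down the same section: "A minimum of 3 data points will be used for" its determination.

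SAP 5.5 admits a participant to the PK analysis set (PKAS) on a lower threshold. The participant must have received VIS954 and "have at least 1 measured post-dose VIS954 serum concentration at a scheduled PK time", with no deviation or event that could affect the PK evaluation.

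SAP 15.1 adds a general clause: "Participants with partial data will be evaluated on a case-by-case basis to determine if sufficient data are available for reliable estimation of PK parameters". It gives no criterion and does not say that it overrides the three-value rule.

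Cmax then feeds the parameter summaries, DNCmax and the plots against dose ("Scatter plots of individual and geometric mean of PK parameters", SAP 15.2). The parameter summaries are also split into Japanese and non-Japanese participants.

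**The concern.** A three-point minimum is natural for a log-linear terminal fit, and λz already has one. For a maximum read from the data it serves no estimation purpose, because one quantifiable value defines it. Under the rule as written, a participant with one or two quantifiable values is in the PKAS and in the concentration tables (with BLQ set to zero, SAP 15.1) but has no Cmax. Two displays built on the same analysis set would then describe different people.

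If the count is below three because most values are BLQ, the omission depends on the outcome being summarized. Low values leave the summary, so the geometric mean Cmax and DNCmax at that dose go up and the lower end of the Cmax-versus-dose plot is lifted, which flattens the apparent dose relation. There are 7 active participants per dose. At the target 5:4 split and with at most one Japanese participant on placebo, each ethnic subgroup has 3 or 4 of them, so losing one person would show.

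**Working it through.** The plan states no figure on this point, so there is none to reproduce. The question is how large the effect could be, and when.

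**Inputs from the documents**
- Postdose PK samples: 4, 8, 24 and 48 h, then Days 5, 8, 11, 15, 22, 29, 36, 43, 57 and 71 (Protocol, Schedule of Activities footnote): 4 + 10 = 14.
- LLOQ: 25 ng/mL = 0.025 µg/mL (SAP 15.1).
- Active participants per dose: 7 (Protocol 4.1).

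**Assumptions.** Doses are redacted, and the readable text gives no predicted exposure, half-life or variability. These were varied.

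**Model and measure.** One-compartment SC profile, C(t) = A · ka/(ka − ke) · (e^(−ke·t) − e^(−ka·t)) with residual error. Let q be the number of the 14 values at or above the LLOQ.

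Excess = GM(Cmax | q ≥ 3) / GM(Cmax | q ≥ 1) − 1

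**Simulation 1.** 40,000 profiles per setting; ka 0.4/day; CV 30% on rate constants and 40% on exposure; residual 10%. Geometric means in ng/mL:

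| True Cmax (× LLOQ) | Half-life | q ≥ 1 | q ≥ 3 | Excess |
|---|---|---|---|---|
| 30 (1.2×) | 1 d | 39.8 | 49.9 | 49.9/39.8 − 1 = 25% |
| 30 | 3 d | 38.9 | 46.2 | 19% |
| 30 | 7 d | 38.6 | 43.6 | 13% |
| 40 (1.6×) | 1 d | 46.8 | 56.1 | 20% |
| 40 | 3 d | 45.9 | 52.3 | 14% |
| 40 | 7 d | 45.5 | 49.6 | 9% |
| 60 (2.4×) | 1 d | 63.4 | 69.8 | 10% |
| 60 | 3 d | 63.1 | 66.9 | 6% |
| 60 | 7 d | 63.2 | 65.3 | 3% |

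A repeat run put the largest value at 26%. At 100 ng/mL (4×) the excess is about 2% or less; at 250 ng/mL (10×) there is none. At 30–40 ng/mL, 15–33% of participants have one or two quantifiable values.

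**Simulation 2, wider assumptions.** 6,000 cohorts of 7 per setting; half-life 24 to 480 h; absorption half-life 29 to 72 h; exposure CV 40% or 70%; log-SD 0.3 on rate constants; residual log-SD 0.15.

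| Median Cmax | Excess in GM Cmax | P(at least 1 of 7 has q = 1 or 2) |
|---|---|---|
| 2 × LLOQ | 4% to 27% | 32% to 91% |
| 3 × | 1% to 17% | 4% to 68% |
| 5 × | 0% to 7% | 0.2% to 29% |
| 10 × | at most 1% | at most 4% |
| 20 × and above | 0 | about 0 |

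The excess was never negative.

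**What the one-value rule leaves behind.** Simulation 2 also gives the excess of the q ≥ 3 mean over all participants, including those with no quantifiable value. Dividing the two factors gives the part that remains under q ≥ 1. At 2 × LLOQ with half-life 24 h and CV 70%: 1.539/1.268 − 1 = 21%. With half-life 480 h and CV 40%: 1.068/1.038 − 1 = 3%. These are the extremes at 2 × LLOQ. Participants with no quantifiable value are still missing, so the change reduces the bias and does not remove it.

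**One cohort of 7, assumed values.** Cmax 0.03, 0.045, 0.08, 0.10, 0.12, 0.15 and 0.20 µg/mL. If the two lowest are dropped, the geometric mean goes from 0.0874 to 0.1236: 0.1236/0.0874 − 1 = 41%.

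**The case against.** The strongest reply is that nothing readable shows a cohort near the LLOQ. With 14 samples out to Day 71 and an LLOQ of 0.025 µg/mL, a median Cmax of 10 × LLOQ makes the effect negligible. The largest percentages also rest on a 1-day half-life that no document supports; sampling to Day 71 and a contraception period that treats systemic exposure as ending at Day 56 suggest longer profiles. This stands, and it is why the point is conditional. A reader might infer that the plan does drop the lowest-exposure participants and does inflate low-dose Cmax. The documents do not support that as a statement of fact.

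A reader might also infer that only low-exposure participants can be lost. That is not so: withdrawal, missed samples or bioanalytical problems can leave fewer than three values at any exposure. Nor is there a contradiction between SAP 5.5 and 15.2. A one-value entry rule for a set that also serves the concentration summaries can coexist with a stricter rule for parameters.

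Some protection exists. The case-by-case clause may rescue a participant, listings cover all treated participants, and N and n are both reported (SAP 15), so a loss would be visible. But visibility does not correct the mean, and discretion without a criterion does not replace a written rule.

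Finally, the consequence is limited. SAP 6.7 plans no hypothesis testing, and the next cohort is opened on the safety monitoring committee's review of safety data (Protocol 9.3).

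**Conclusion.** The point holds in conditional form. On its wording, SAP 15.2 withholds Cmax, tmax and DNCmax from a PKAS participant with one or two quantifiable values, without need. If a cohort's exposure lies within about 5 × LLOQ (5 × 25 = 125 ng/mL), participants in that position because of low exposure would be lost and the descriptive geometric mean Cmax would be biased upward, by the amounts in Simulation 1 for half-lives of 1 to 7 days. Higher variability extends the range somewhat; from about 10 × LLOQ the rule makes practically no difference.

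The size rests on assumed one-compartment kinetics, half-lives and variability. Target-mediated clearance and anti-drug antibodies were not modelled, beyond the short half-life settings. The sponsor knows the doses and can settle whether the condition is met. This is a minor, inexpensive correction to descriptive PK output. The body of SAP 15.3 is not readable, so nothing is claimed about any analysis described there.

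**What to change.** In SAP 15.2:

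1. Limit the three-quantifiable-value minimum to AUC0-last, λz and the parameters derived from λz (t1/2, AUC0-inf, CL/F, Vd/F), and to the dose-normalized AUCs. AUC0-last needs naming because it does not depend on λz and would otherwise have no minimum.
2. Report Cmax, tmax and DNCmax for every PKAS participant with at least one quantifiable postdose value.
3. Show, per dose, the number of participants with no quantifiable value and the number with one or two, with a note that the geometric mean Cmax still excludes those with none.

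Cost: a sentence or two in the SAP, plus two count rows and a footnote in the Cmax table. The downside is that a Cmax or tmax resting on one or two values is less precise, so flag it in the listing. If every cohort is well above the LLOQ, the results do not change for that reason; the rule would then matter only for participants with missing samples.

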# 3. STUDY DESIGN

# 3.1. General Description

This is a phase 1, randomized, placebo-controlled, double-blind, single ascending dose, first-in-human (FIH) study to assess the safety, tolerability, PK, and PD of VIS954 administered subcutaneously (SC) in healthy participants.

The study will be conducted in 6 sequential cohorts. Each cohort will enroll 9 participants, randomized to VIS954 or placebo at a ratio of 7:2 (7 VIS954:2 placebo). Eligible participants will be centrally assigned to randomized study intervention. Before the study is initiated, information and directions for the randomization will be provided to the trial site unblinded pharmacist. Each cohort will also optimally enroll 5 non-Japanese participants and 4 Japanese participants (achievement of this ratio is desired but not mandatory to advance to the next cohort). No more than one Japanese participant per cohort may be randomized to receive placebo.

Sentinel participants will be utilized in each cohort; the first 2 non-Japanese participants in each cohort will be randomized to receive either VIS954 (n = 1) or placebo (n = 1) and will receive the study intervention at least 24 hours before the remaining 7 participants in the cohort are dosed. The safety data from each of the 2 sentinel participants will be reviewed over the 24-hour post-administration period to determine whether it is appropriate to proceed with dosing of the remaining participants in the cohort as planned. A similar review will occur for each dose escalation. The remaining 7 participants in a cohort will be randomized to receive VIS954 (n = 6) or placebo (n = 1).

Escalation to next dosing level will occur after review of blinded safety data when at least 7 participants have completed  $\geq$  14 days in a cohort.

The planned dose of VIS954 for each cohort is summarized in Table A below. For more information, refer to Section 4.1 of the clinical study protocol.

Page 14 of 42

Statistical Analysis Plan

Table A: Planned dose of VIS954 for each cohort

Study Intervention for Each Cohort		
Cohort	Study Intervention	
Cohort 1	VIS954 or placebo	
Cohort 2	VIS954 or placebo	
Cohort 3	VIS954 or placebo	
Cohort 4	VIS954 or placebo	
Cohort 5	VIS954 or placebo	
Cohort 6	VIS954 or placebo	

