### 15. PHARMACOKINETIC ANALYSIS

Pharmacokinetic concentration and parameter listings will include data for all treated participants. Descriptive statistic summaries and figures for PK analysis (serum) will be based on the PKAS. Summary statistics for PK concentrations and parameters will be presented for all participants in each dose level and by Japanese versus non-Japanese; Additionally, summary statistics for PK concentrations will be presented for all participants in each dose level and by ADA status (positive and negative). The summary statistics will include N, n, mean, SD, median, minimum, maximum, CV%. Geometric mean and geometric CV% will be presented for PK parameters, except for tmax for which only N, n, median, minimum, and maximum will be reported.

Visterra Insert
Customer Name/ Logo
Protocol VIS954-101
Page 25 of 42

Statistical Analysis Plan

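### SAP 15.2: the adjusted R-squared exclusion names AUC0-inf and t1/2 but not CL/F and Vd/F, which rest on the same rejected λz

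*SAP*

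**What the plan says.** SAP 15.2 defines AUC0-inf as AUC0-last plus Clast/λz, t1/2 as ln2/λz, CL/F as dose over AUC0-inf, and Vd/F as dose over the product of λz and AUC0-inf. It also lists "Dose normalized AUC 0-inf" as an estimated parameter. For the λz regression, "A minimum of 3 data points will be used for determination".

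Three exclusion rules in 15.2 bear on the summaries:

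- **Adjusted R-squared.** If the "Adjusted Rsq value is less than 0.800 then AUC 0-inf and t 1/2 will be listed but" not summarized. No other parameter is named.
- **%AUCex above 20%.** AUC0-inf is listed only, and the rule goes on: "Associated parameters (CL/F and V d /F) will be listed but not included in summary statistics as well". DNAUC0-inf is not named.
- **Predose value above 5% of Cmax.** Here "the PK parameters for the given participant will be calculated and reported in the listing but excluded from statistical summaries and analyses".

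The default is inclusion: "Pharmacokinetic parameters will be summarized by each cohort and by Japanese versus non-Japanese within each active treatment group using descriptive statistics". SAP 15 adds that "Geometric mean and geometric CV% will be presented for PK parameters, except for t max". CL/F, Vd/F and DNAUC0-inf are in the main parameter list, not in the diagnostic group that is listed without being summarized. CL/F and Vd/F are named secondary endpoints in SAP 2.2; DNAUC0-inf is not.

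**The concern.** A low adjusted R-squared means that λz is too poorly determined for AUC0-inf and t1/2 to be summarized. CL/F is dose divided by that AUC0-inf. Vd/F equals CL/F × t1/2 / ln2, so both of its ingredients have just been rejected. A programmer who compares this rule with the %AUCex rule, which does name CL/F and Vd/F, could reasonably keep them in.

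A PK table could then show a larger n for CL/F and Vd/F than for AUC0-inf and t1/2, with rejected fits inside the Vd/F mean and CV%. The summaries are small: seven active participants per dose, and three or four in each Japanese/non-Japanese subgroup if the desired 5:4 split is met.

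**Working it through.** The plan states no figure for this rule, so there is none to reproduce. The inputs from SAP 15.2 are the 0.800 and 20% thresholds, the three-point minimum and the parameter definitions. SAP 3.1 gives the cohort sizes. The true extrapolated fraction e is not in the documents; 5–15% is assumed. AUC0-last and Clast are treated as correct, so that only the λz error acts.

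**Precision of λz at the threshold.** For a straight-line fit to n points, with t = λz/SE:

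- R² = t²/(t² + n − 2), and adjusted R² = 1 − (1 − R²)(n − 1)/(n − 2).
- Setting adjusted R² = 0.800 gives t² = 4n − 3.
- n = 3: t = 3.00, SE/λz = 33%. n = 4: t = 3.61, 28%. n = 5: t = 4.12, 24%.
- With three points (1 residual df), ±1 SE has 50% nominal coverage, so a one-SE error is not a tail event.

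**Effect on the parameters.** Let k = estimated/true λz.

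- AUC0-inf ratio A = 1 − e + e/k (the same for DNAUC0-inf).
- CL/F ratio = 1/A. Vd/F ratio = 1/(kA). %AUCex = (e/k)/A.

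For n = 3, a true λz one SE above or below the estimate gives k = 1/1.333 = 0.75 (underestimated) or k = 1/0.667 = 1.5 (overestimated):

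| e | Vd/F, k = 0.75 / 1.5 | CL/F | %AUCex |
|---|---|---|---|
| 5% | +31.1% / −32.2% | −1.6% / +1.7% | 6.6% / 3.4% |
| 10% | +29.0% / −31.0% | −3.2% / +3.4% | 12.9% / 6.9% |
| 15% | +27.0% / −29.8% | −4.8% / +5.3% | 19.0% / 10.5% |

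At e = 10%: A = 0.90 + 0.10/0.75 = 1.033, and the Vd/F ratio is 1/(0.75 × 1.033) = 1.290. DNAUC0-inf moves by the same small amounts as AUC0-inf, about 2–5%. With more points at e = 10%, Vd/F moves +24.3%/−25.7% (n = 4) or +21.3%/−22.4% (n = 5).

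**Does the 20% rule step in?** It is reached at e = 0.2/(0.8/k + 0.2).

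- At adjusted R² = 0.800, n = 3, one SE: e = 15.8% (k = 0.75) or 27.3% (k = 1.5). Throughout the assumed range the rule stays silent.
- At adjusted R² = 0.70: R² = 0.85, t² = 5.67, SE/λz = 0.42. With e = 15% and λz underestimated, %AUCex is 20.0%.
- At adjusted R² = 0.60: R² = 0.80, t² = 4, SE/λz = 0.50, k = 0.667. With e = 15%, A = 1.075 and %AUCex = 0.225/1.075 = 20.9%, so the rule acts. If λz is overestimated instead, k = 2, A = 0.925 and %AUCex = 0.075/0.925 = 8.1%, so it does not.

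**Effect on a summary.** One three-point value at e = 10% (ratio r = 1.290 or 0.690) changes a geometric mean by r^(1/n) − 1:

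- n = 7: +3.7% / −5.2%
- n = 4: +6.6% / −8.9%
- n = 3: +8.9% / −11.6%

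The subgroup sizes assume the 5:4 split is met. One non-Japanese sentinel receives placebo, and "No more than one Japanese participant per cohort may be randomized to receive placebo". The second placebo is therefore either Japanese (3 Japanese and 4 non-Japanese active) or non-Japanese (4 and 3).

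**The case against.** No sentence in the SAP says that CL/F and Vd/F are kept. That is inferred from silence plus the general summary statement. SAP 8 leaves output content to templates that are not supplied, and the text of 15.3 is not visible. This stands as a limit: the finding concerns the visible wording only.

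Safeguards exist. The terminal phase is chosen by eye before λz is fitted, and SAP 15.1 reviews participants with partial data case by case. The schedule has ten PK samples from Day 5 to Day 71, so fits with more than three points may be available. These make bad cases less likely, but none of them says what happens to CL/F and Vd/F once adjusted R-squared falls below 0.800.

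A reader might infer that the omission is a proven slip, because the neighbouring rules go further. The support is partial. The predose rule excludes the participant's parameters as a whole rather than following a chain of dependence, and the %AUCex rule itself leaves out DNAUC0-inf. An unintended omission is plausible but not shown.

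A reader might also infer that the 20% rule never catches these cases. That holds over the assumed range only at the threshold with a one-SE error. Further below 0.800, with λz underestimated and extrapolation near 15%, the rule begins to act.

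Finally, DNAUC0-inf is AUC0-inf divided by dose, so excluding AUC0-inf can fairly be read as covering it. Naming it is a matter of consistency.

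**Conclusion.** The gap is real on the visible text. When adjusted R-squared is below 0.800, CL/F and Vd/F remain in the summaries unless %AUCex also exceeds 20%. That second rule measures how much of the AUC is extrapolated, not how well λz is fitted. It is a partial backstop and does not catch most overestimated λz.

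Only Vd/F is materially exposed, at roughly 30% for an individual value in the three-point threshold case. This rests on the assumed 5–15% extrapolation and a one-SE error. It would be wrong to read the same size into CL/F.

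Severity is minor. The affected outputs are descriptive secondary summaries, the median is largely unaffected, individual values are listed, and no hypothesis test is planned. Nothing in the documents ties dose escalation to these summaries. How often the rule would fire cannot be established from the documents, and no frequency is claimed.

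**What to change.** In SAP 15.2, extend the adjusted R-squared rule so that CL/F and Vd/F join AUC0-inf and t1/2 as listed but not summarized. For consistency, name DNAUC0-inf in both that rule and the %AUCex rule. Check that the output templates and 15.3 agree, and settle the wording before unblinding so that no choice of values is made after the data are seen.

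The cost is a few words, with no new data or analysis. Each participant caught by the rule gives one fewer summarized value of each added parameter: one of up to seven per dose, or one of three or four in a subgroup. For CL/F and DNAUC0-inf that loss buys agreement with AUC0-inf rather than removal of a large error. All values remain in the listings.
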